10.2 Sample Size and Accrual

Up to 49 patients (Arm A=24, Arm B=25) will be entered into the trial based on optimal Simon two stage design as below.

Arm A: In the first stage, 9 patients will be entered. If no patients show a response, then the trial will be terminated due to inactivity of the treatment. If 1 or more of 9 show a response, then an additional 15 patients will be added. If 2 or fewer of 24 show a response, then the trial will conclude that the response rate could be as low as 5%. If 3 or more respond, then the trial will conclude that the response rate is at least 20%. This design has a 20% chance of falsely concluding the rate is 5% (false negative Type II error rate = 20%, or power = 80%), and a 10% chance of falsely concluding that the rate is 20% (false positive Type I error rate = 10%). There is a 63% probability of early termination of the trial when the true response rate is 5%.

Arm B: In the first stage, 12 patients will be entered. If 2 or less patients show a response, then the trial will be terminated due to inactivity of the treatment. If 3 or more of 12 show a response, then an additional 13 patients will be added. If 7 or fewer of 25 show a response, then the trial will conclude that the response rate could be as low as 20%. If 8 or more respond, then the trial will conclude that the response rate is at least 40%. This design has a 20% chance of falsely concluding the rate is 20% (false negative Type II error rate = 20%, or power = 80%), and a 10% chance of falsely concluding that the rate is 40% (false positive Type I error rate = 10%). There is a 56% probability of early termination of the trial when the true response rate is 5%.

Due to inevaluable patients and dropout, target accrual will be 51 patients. It is anticipated that 2 patients will be accrued per month so that accrual to this study will take 2 years.

Thus, this study will be a single institution trial with duration of enrollment being 2 years. The study will be done via both internal and external referral system. Being one of the busiest lung cancer programs in the area with good advertisement plan towards partnering institutions on this clinical trial, the above accrual plan is deemed to be a feasible one.

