Sample Size	
Up to 51 patients (minimum of 21 patients)
 
Based on optimal Simon two stage design;
 
 - Arm A: If stopped earlier 9 patients will be enrolled to arm A, if continued, 24 patients will be enrolled. - Arm B: If stopped earlier 12 patients will be enrolled to arm B, if continued 25 patients will be enrolled. 
Total maximum number of evaluable patients=49
 
Given possible inevaluable patient and drop out from study, we will aim for 51 patients for total enrollment.
 
This will be a single institution trial with duration of enrollment estimated to be 2 years.
 
Estimated accrual rate will 25.5 per year, approximately 2 per month.

NU Study Number: NU 16L04
Other Study Number: CA 209-801

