Treatment Plan	
Patients will start metformin (Glucophage XR) at 1,000mg by mouth once daily during a 7-day induction period prior to starting nivolumab Cycle 1 Day 1 (1 cycle = 28 days). The dose will be increased by 500mg every 7 days (C1D1 and C1D8) until reaching the target dose of 2000mg. Nivolumab will be administered at a fixed dose of 240 mg IV every 14 days during Cycle 1-4 (Day 1 & 15) and 480mg IV every 28 days starting with Cycle 5 Day 1. Treatment will continue until disease progression confirmed by RECIST criteria v1.1, intolerable toxicity or withdrawal of consent. Imaging by CT or MRI will be scheduled every 2 cycles (8 weeks).

NU Study Number: NU 16L04
Other Study Number: CA 209-801

Statistical Methodology	
Accounting for invaluable patients and dropouts, up to 51 patients (Arm A=24, Arm B=25) will be entered into the trial based on optimal Simon two stage design as below.
 
Arm A: In the first stage, 9 patients will be entered. If no patients show a response, then the trial will be terminated due to inactivity of the treatment. If 1 or more of 9 show a response, then an additional 15 patients will be added. If 2 or fewer of 24 show a response, then the trial will conclude that the response rate could be as low as 5%. If 3 or more respond, then the trial will conclude that the response rate is at least 20%. This design has a 20% chance of falsely concluding the rate is 5% (false negative Type II error rate = 20%, or power = 80%), and a 10% chance of falsely concluding that the rate is 20% (false positive Type I error rate = 10%). There is a 63% probability of early termination of the trial when the true response rate is 5%.
 
Arm B: In the first stage, 12 patients will be entered. If 2 or fewer patients show a response, then the trial will be terminated due to inactivity of the treatment. If 3 or more of 12 show a response, then an additional 13 patients will be added. If 7 or fewer of 25 show a response, then the trial will conclude that the response rate could be as low as 20%. If 8 or more respond, then the trial will conclude that the response rate is at least 40%. This design has a 20% chance of falsely concluding the rate is 20% (false negative Type II error rate = 20%, or power = 80%), and a 10% chance of falsely concluding that the rate is 40% (false positive Type I error rate = 10%). There is a 56% probability of early termination of the trial when the true response rate is 5%.

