Group A and Group B will address two clinical questions. Group A is designed to assess possible synergistic effect of the combination treatment in immunotherapy naïve patients whereas group B is designed to determine whether the combination treatment of metformin with immunotherapy can overcome resistance to single agent PD-1/PD-L1 inhibitors.

Group A: In order to demonstrate synergy in anti-tumor effect, ORR of the combination treatment will be compared to that of historical control (20%) reported in phase 3 single agent nivolumab trials in lung cancer (CheckMate057 and CheckMate017). Optimal Simon's two stage design will be used with target ORR of 40% versus control ORR of 20% (type 1 error rate of 0.1 and power of 0.8)

Group B: In order to find signal in patients with prior exposure to single agent PD-1/PD-L1 inhibitors, ORR of the combination treatment will be described. Optimal Simon's two stage design will be used with target ORR of 20% versus control ORR of 5% (type 1 error rate of 0.1 and power of 0.8).

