10.3 Data Analyses Plans

Summary of Analytic plan for primary objective	Summary of Analytic plan for secondary objectives

Please refer to the below sample size justification for the parallel Simon's two stage design which defines how the endpoints are met.
 
For Group A. Estimated ORR for historical control is 20% versus target ORR of 40% for nivolumab and metformin combination treatment.
	
Depth of response: waterfall plot Duration and persistence of response: swimmer's plot PFS: PFS at 1 and 2 years (Kaplan-Meier analysis) OS: OS at 1 and 2 years (Kaplan-Meier analysis) ORR, DCR by irRC (descriptive statistics,

NU Study Number: NU 16L04
Other Study Number: CA 209-801

For Group B. Estimated ORR for refractory patients is 5% versus target ORR of 40% for niovulomab and metformin combination treatment.
	
exact binomial confidence intervals) We will use descriptive statistics and graphical displays to evaluate change in serum biomarkers between pre- and post-treatment. A Wilcoxon signed rank test will be used to determine if there is a statistically significant change in serum biomarkers. Toxicities will be tabulated by type and grade.

--	---

The primary analysis will be on the evaluable analysis set, including all evaluable patients regardless of drug exposure. Clinical benefit rate will be defined as stable disease (for ≥ 12 weeks), complete or partial response by both the Response Evaluation Criteria in Solid Tumors (RECIST) and irRECIST. Maximum response prior to disease progression will be used. The overall response rate will be estimated by the proportion of overall response, and its 80% confidence interval (CI) and 95% CI will be estimated using the exact binomial distribution.

Additionally, we will evaluate overall response rate, defined as complete or partial response using RECIST guidelines in a similar manner. We will also perform similar analyses using Immune Related RECIST (irRECIST). Duration of response, defined as the duration from the first documentation of clinical benefit to the first documented progressive disease or death of any cause, whichever occurs first, will also be analyzed. For patients alive and progression-free at the time of data cut off, duration of response will be censored as of the last tumor assessment date. Duration of response will only be evaluated for the subgroup of patients with a clinical benefit using the Kaplan-Meier method.

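### The two-stage decision rules are attached to the wrong arms, giving Arm A about 80% type I error at its 20% historical control and Arm B about 10% power at its 20% target

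*Combined protocol and SAP*

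**What the plan says.** Inclusion criterion 3.1.3 defines Arm A as naive to PD-1/PD-L1 inhibitors and Arm B as refractory to, or progressed on, one of them. Section 1.3.2 uses Group A and Group B for the same populations.

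**Hypotheses.** Section 1.3.2 compares Group A with the response rate in phase 3 trials of single-agent nivolumab, with "target ORR of 40% versus control ORR of 20" percent. For Group B it gives "target ORR of 20% versus control ORR of 5" percent. Both use type I error 0.10 and power 0.80. Section 10.3 agrees for Group A: "Estimated ORR for historical control is 20% versus target ORR of 40% for nivolumab and metformin combination treatment". For Group B it keeps the 5% null but changes the target: "Estimated ORR for refractory patients is 5% versus target ORR of 40" percent.

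**Decision rules.** Section 10.2 and the Statistical Methodology row of the Study Summary give these rules:
- Arm A: stop if there are no responses in 9 patients, otherwise continue to 24. "If 2 or fewer of 24 show a response, then the trial will conclude that the response rate could be as low as 5" percent; 3 or more responses are read as a rate of at least 20%.
- Arm B: stop at 2 or fewer of 12, otherwise continue to 25. "If 7 or fewer of 25 show a response, then the trial will conclude that the response rate could be as low as 20" percent; 8 or more responses are read as a rate of at least 40%.

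The Sample Size row of the Study Summary repeats the arm sizes: "Arm A: If stopped earlier 9 patients will be enrolled to arm A, if continued, 24 patients will be enrolled". For Arm B, section 10.2 adds: "There is a 56% probability of early termination of the trial when the true response rate is 5" percent.

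**The concern.** The null and target rates behind each arm's rule are those that section 1.3.2 assigns to the other arm. These rules decide whether each arm continues and whether it is called positive on the primary endpoint.

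Arm A is meant to show synergy over single-agent nivolumab. As written it succeeds with 3 of 24 responses (12.5%), which is below the protocol's own 20% benchmark. Arm B is meant to find a signal in resistant disease. As written it would usually be abandoned at stage 1 even if the combination reached its 20% target.

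**Working it through.** **Inputs.** Rules from section 10.2: Arm A, r1 = 0, n1 = 9, r = 2, n = 24; Arm B, r1 = 2, n1 = 12, r = 7, n = 25. Rates from section 1.3.2: Group A 20% versus 40%; Group B 5% versus 20%.

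**Formulas.** With X1 ~ Bin(n1, p) and X2 ~ Bin(n − n1, p):
- P(stop early) = P(X1 ≤ r1)
- P(declare active) = Σ over x1 > r1 of P(X1 = x1) × P(X2 ≥ r + 1 − x1)

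**Step 1: reproduce the plan's figures.** An exhaustive search for the Simon optimal design with type I error at most 0.10 and power at least 0.80 returns exactly the two rules in section 10.2.

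| Rates | Optimal rule | Type I error | Power | Early stop at the null |
|---|---|---|---|---|
| 5% vs 20% | 0/9, 2/24 | 9.3% | 80.5% | 63.0% |
| 20% vs 40% | 2/12, 7/25 | 9.9% | 81.5% | 55.8% |

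These are the two pairs of rates in section 1.3.2. The designs were computed correctly, and the fault lies in their assignment to arms.

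**Step 2: Arm A's written rule at its null of 20%.**
- Stop at stage 1: 0.8^9 = 0.1342.
- One response in stage 1, then at most one in 15: (9 × 0.2 × 0.8^8) × (0.8^15 + 15 × 0.2 × 0.8^14) = 0.3020 × 0.1671 = 0.0505.
- Two responses in stage 1, then none in 15: (36 × 0.2² × 0.8^7) × 0.8^15 = 0.3020 × 0.0352 = 0.0106.
- P(not declared active) = 0.1342 + 0.0505 + 0.0106 = 0.1953.
- P(declared active) = 1 − 0.1953 = **0.8047**, against a stated type I error of 0.10.

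**Step 3: Arm B's written rule at its target of 20%.**
- Stop at stage 1: 0.8^12 + 12 × 0.2 × 0.8^11 + 66 × 0.2² × 0.8^10 = 0.0687 + 0.2062 + 0.2835 = **0.558**.
- P(declared active), from the full sum = **0.0991**, against a stated power of 0.80.

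**Step 4: the 56% sentence for Arm B.** At the stated true rate of 5%, the stage 1 stopping probability is 0.95^12 + 12 × 0.05 × 0.95^11 + 66 × 0.05² × 0.95^10 = 0.5404 + 0.3413 + 0.0988 = **0.980**. The 56% is the value at 20% (step 3).

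**Step 5: the 40% target for Group B in section 10.3.** At a true 40%, Arm B's written rule has power 81.5%. At the 5% null in the same sentence, its type I error is about 0.00002. The optimal design for 5% versus 40% would be 0/4, 1/8, with only 8 patients, so neither written rule was built for that pair.

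**The case against.** **The Arm B power figure is conditional.** It depends on the 20% target in section 1.3.2. Under section 10.3's 40% target, the written rule has 81.5% power. That is correct, and the 9.9% should always be quoted with its condition. It does not rescue the rule, because section 10.3 keeps a 5% null for Group B while the written rule tests against 20%. The Arm A figure has no such weakness: sections 1.3.2 and 10.3 agree on its 20% null.

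**Section 10.2 might be the intended text.** Against its own 5% null, Arm A's rule has 9.3% type I error, and the Study Summary agrees with section 10.2. The direction of the correction is therefore an inference, but a strong one. Only section 1.3.2 gives reasons, and a test of synergy over single-agent nivolumab needs a null at the single-agent rate. Nothing in the protocol supports a 5% null for naive patients or a 20% null for refractory ones. If section 10.2 were kept, sections 1.3.2 and 10.3 would both have to be rewritten.

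**Group B's response rate is only to be described.** Section 1.3.2 does use that word, but it also states an error rate and a power for the arm, so the rule still has to deliver them.

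**Changing the rules may not be simple.** This stands. The current version is Amendment 5 and the change log begins in January 2017, so patients may already be enrolled. The documents do not give accrual status.

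**Conclusion.** The concern holds and must be fixed. The rules in section 10.2 and the Study Summary are exchanged relative to the hypotheses in section 1.3.2, and no other section or amendment entry resolves this.

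- Arm A, true response rate 20% (metformin adds nothing): declared active 80.5% of the time, against a stated 10%.
- Arm B, true response rate 20% (the target in section 1.3.2): declared active 9.9% of the time, against a stated 80%, with 55.8% stopping at stage 1.
- Arm B early termination at a true 5%: 98.0%, against the stated 56%.

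The results use exact binomial probabilities and assume that the rules are applied literally to the planned numbers of evaluable patients. They take section 1.3.2 as the intended hypotheses; the sponsor should confirm this.

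**What to change.** In section 10.2 and in both the Sample Size and Statistical Methodology rows of the Study Summary, exchange the rules:
- Arm A (20% versus 40%): 12 patients, stop at 2 or fewer responses; otherwise continue to 25, success at 8 or more. Type I error 9.9%, power 81.5%, early stop 55.8% at a true 20%.
- Arm B (5% versus 20%): 9 patients, stop at 0 responses; otherwise continue to 24, success at 3 or more. Type I error 9.3%, power 80.5%, early stop 63.0% at a true 5%.

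State the 56% early-termination probability at a true rate of 20%. Correct the Group B target in section 10.3 to 20%. Change the stated arm sizes to A = 25 and B = 24.

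The totals do not move: the minimum stays 9 + 12 = 21 and the maximum 24 + 25 = 49. If no stage 1 decision has been taken, the cost is a protocol amendment, with the stage 1 look moving from 9 to 12 patients in Arm A and from 12 to 9 in Arm B. If either arm has enrolled, the amendment should state which rule was applied and whether a stage 1 decision was made, with review by the trial statistician and the DSMC. Exchanging the labels after an interim look would not by itself restore the stated error rates.

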1.3 Rationale for the Current Study

1.3.1 Generating synergy and overcoming resistance to PD-1/PD-L1 inhibitors with the combination of nivolumab and metformin:

Building upon the above scientific and clinical rationale supporting the use for metformin to maximize the benefit of immunotherapy and the high unmet need for more effective treatment options for patients with non-small cell lung cancer both with and without prior exposure to PD-1/PD-L1 inhibitors, we propose a proof-of-concept parallel phase 2 trial using the combination regimen of nivolumab and metformin.

We hypothesize that the combination of nivolumab and metformin will be synergistic in effect and also will overcome the resistance to single agent PD-1/PD-L1 inhibitors. The fact that metformin activates CD8+ TILs, aids in formulation of TEMs and suppress Tregs at the same suggests that the combination of metformin and anti-PD1 monoclonal antibody, nivolumab may exert more robust immune modulatory anti-cancer effect than single agent PD-1/PD-L1 inhibitors. In addition, non-immune anti-tumor property of metformin may have assist in providing additive anti-cancer effect.

In Group B, this trial will enroll both patients who initially responded to PD-1/PD-L1 inhibitors and progressed later on as well as patients had primary refractoriness to such agents. This trial will also serve as a proof of concept trial to later further explore the effectiveness of the metformin- immune check-point inhibition combination regimen in cancers that harbor primary or secondary resistance to PD-1/PD-L1 inhibitors.

Given that the indications for PD-1/PD-L1 inhibitors in solid cancers will only expand in the near future, time is right for this proof-of-concept trial that will answer the important clinical questions in both increasing efficacy and overcoming the resistance in PD-1/PD-L1 inhibitors. This trial may pave way for the next pivotal phase 3 trial in non-small cell lung cancer or for proof of concept phase 2 trial in other cancer types where the combination treatment may be of significant clinical value.

1.3.2 Rationale for the Study Design:

NU Study Number: NU 16L04
Other Study Number: CA 209-801

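### A go is worded as showing a response rate of at least 20% or 40%, but the two Simon designs can only show that it exceeds 5% or 20%

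*Combined protocol and SAP*

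**What the plan says.** Section 10.2 sets out two optimal Simon two-stage designs, and the Statistical Methodology row of the Study Summary repeats them.

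- **Design 1** (labelled Arm A there): stop at 0 of 9, otherwise go on to 24. "If 3 or more respond, then the trial will conclude that the response rate is at least 20"%. The error statement is "a 10% chance of falsely concluding that the rate is 20% (false positive Type I error rate = 10"%).
- **Design 2** (labelled Arm B there): stop at 2 or fewer of 12, otherwise go on to 25. "If 8 or more respond, then the trial will conclude that the response rate is at least 40"%. The error statement is "a 10% chance of falsely concluding that the rate is 40% (false positive Type I error rate = 10"%).

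The no-go conclusions are more guarded: they say only that the rate might be as low as 5% or 20%.

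Section 1.3.2 describes the same kind of design as a test of a target against a control: "Optimal Simon's two stage design will be used with target ORR of 40% versus control ORR of 20"%, with type I error 0.1 and power 0.8. It gives 20% against 5% for the other group.

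Section 10.3 refers to the two-stage design as the definition of when the endpoint is met. It also plans exact 80% and 95% confidence intervals for the response rate.

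**The concern.** A Simon design that rejects its null at one-sided 10% supports one statement: the rate is above the null. The alternative is only the rate at which the design has its planned power. Section 10.2 turns that alternative into a demonstrated lower limit and places a 10% false-positive rate beside it.

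This is the prespecified conclusion for the primary endpoint. Section 1.3.1 looks ahead to confirmatory work: "This trial may pave way for the next pivotal phase 3 trial in non-small cell lung cancer". A reader planning that work could take 20% or 40% as a floor established with 10% error, when the data need only have excluded 5% or 20%.

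**Working it through.** **Inputs (section 10.2).** Design 1: r1 = 0, n1 = 9, r = 2, n = 24, null 5%, target 20%. Design 2: r1 = 2, n1 = 12, r = 7, n = 25, null 20%, target 40%. Both: type I error 10%, power 80%.

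**Formula.** With X1 the stage 1 responders and X2 the stage 2 responders,

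P(go | p) = Σ over x1 > r1 of P(X1 = x1; n1, p) × P(X2 ≥ r + 1 − x1; n − n1, p).

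**Step 1: reproduce the plan's figures.**

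| | P(go) at null | P(go) at target | P(stop early) at null |
|---|---|---|---|
| Design 1 | 9.3% at 5% | 80.5% at 20% | 63.0% |
| Design 2 | 9.9% at 20% | 81.5% at 40% | 55.8% |

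A search for the smallest expected sample size under the null, with type I error at most 10% and power at least 80%, returns exactly these two designs. The boundaries and sample sizes are sound, and the 10% belongs to nulls of 5% and 20%.

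**Step 2: compare the pass mark with the claim.** 3/24 = 12.5% and 4/24 = 16.7% both lead to a claim of at least 20%. 8/25 = 32% and 9/25 = 36% both lead to a claim of at least 40%. The share of go results with an observed rate below the claimed one is:

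- Design 1: 78% at a true 10%; 36% at a true 20%.
- Design 2: 59% at a true 30%; 30% at a true 40%.

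**Step 3: chance of making the claim when it is false.**

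Design 1 at p = 0.15:
- x1 = 1: 0.3679 × 0.6814 = 0.2507
- x1 = 2: 0.2597 × 0.9126 = 0.2370
- x1 ≥ 3: 0.1409 × 1 = 0.1409
- Sum: 0.629 after rounding.

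Design 2 at p = 0.35:
- x1 = 3: 0.1954 × 0.4995 = 0.0976
- x1 = 4: 0.2367 × 0.7217 = 0.1708
- x1 = 5: 0.2039 × 0.8868 = 0.1808
- x1 = 6: 0.1281 × 0.9704 = 0.1243
- x1 = 7: 0.0591 × 0.9963 = 0.0589
- x1 ≥ 8: 0.0255 × 1 = 0.0255
- Sum: 0.658.

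| Design 1, claim ≥ 20% | P(claim) | Design 2, claim ≥ 40% | P(claim) |
|---|---|---|---|
| true 5% | 9.3% | true 20% | 9.9% |
| true 10% | 36.4% | true 30% | 45.6% |
| true 15% | 62.9% | true 35% | 65.8% |
| true 19% | 77.7% | true 39% | 78.8% |
| just below 20% | 80% | just below 40% | 81% |

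**Step 4: what the worded claim would need.** Keep the same stages and require P(continue and total ≥ x) ≤ 10% at the claimed rate.

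- At 20%: x = 7 gives 18.7% and x = 8 gives 8.9%, so 8/24 (33%).
- At 40%: x = 13 gives 15.4% and x = 14 gives 7.8%, so 14/25 (56%).

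These numbers only measure the distance between the claim and the evidence. They are not suggested boundaries.

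**Step 5: the planned intervals at the smallest go result (Clopper-Pearson).**

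- 3/24: 80% interval 4.7% to 25.8%; 95% interval 2.7% to 32.4%.
- 8/25: 80% interval 19.6% to 46.7%; 95% interval 14.9% to 53.5%.

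Neither lower limit comes near 20% or 40% respectively.

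**The case against.** The strongest reply is that section 10.2 uses a familiar two-point shorthand. If the truth can only be the null or the target, then declaring the target when the null holds is the type I error, and 10% is a correct ceiling for it. Section 1.3.2 gives the formal version. The sentences sit in a sample-size justification, and the results will carry exact intervals, so a reader would see 12.5% with a 95% interval of 2.7% to 32.4% and would not be misled. On this view, the 63% and 66% are simply the power of the design between null and target, which is high for any Simon design, and five points is an arbitrary distance.

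Much of this stands. The planned intervals limit the harm, the go/no-go decision is the same either way, and no passage ties a phase 3 decision to the worded claim. The percentages measure the wording fault and are not a second error.

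The reply does not rescue the wording. *At least* is a statement about a range of rates, not about two points, and the 10% does not hold over that range. Nothing in the documents withdraws or qualifies the conclusion. Publishing it beside the planned intervals would put two contradictory statements in one report.

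**Conclusion.** The concern holds. A go in design 1 supports a rate above 5%, and a go in design 2 a rate above 20%, each at one-sided 10% (exact 9.3% and 9.9%). The prescribed conclusions of at least 20% and at least 40% are not supported. Their false-claim probability rises from about 10% at the null to 63% and 66% five points below the claim, and to just over 80% immediately below it.

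The figures assume binomial responses, full enrolment of 24 or 25 evaluable patients, and the boundaries as stated. They apply to each design whichever arm uses it. The fault lies in the stated inference and its error rate; design, sample size and decision rule are unaffected. It should be corrected because it is the primary-endpoint conclusion.

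**What to change.** In section 10.2 and in the Statistical Methodology row of the Study Summary:

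1. Replace the go conclusions with: the response rate exceeds 5% (3 or more of 24), and the response rate exceeds 20% (8 or more of 25).
2. Define the 10% as the maximum chance of a go when the true rate is 5% (or 20%), and the 20% as the maximum chance of no go when the true rate is 20% (or 40%).

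Section 10.2 attaches these designs to the arms the opposite way round from section 1.3.2, and section 10.3 gives Group B a 5% versus 40% pair that matches neither design. That needs separate reconciliation. It touches the same sentences, so both edits are best made together.

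Optionally, add a sentence to section 10.3 that the Simon rule governs the decision. At exactly 3/24 and 8/25 the planned 80% interval just includes the rejected null (lower limits 4.7% and 19.6%). A one-sided 90% lower bound that follows the two-stage sampling, found by solving P(go | p) = 0.10, gives 5.2% and 20.04% and could be shown beside it.

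The cost is wording in two places. The only loss is a less favourable headline after a go.

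### Arm B's 56% early-termination probability is quoted at a true response rate of 5%, but it is the value at 20%; at 5% the printed rule stops 98% of the time

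*Combined protocol and SAP*

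**What the plan says.** Section 10.2 sets out the Arm B design in one paragraph. The first stage is "Arm B: In the first stage, 12 patients will be entered", with the stopping rule "If 2 or less patients show a response, then the trial will be terminated due to inactivity of the treatment". Otherwise the arm expands: "If 3 or more of 12 show a response, then an additional 13 patients will be added". The final decision has a null of 20% ("If 7 or fewer of 25 show a response, then the trial will conclude that the response rate could be as low as 20"%) and a target of 40% ("If 8 or more respond, then the trial will conclude that the response rate is at least 40"%). Type I error is given as 10% and power as 80%.

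The paragraph closes with the early-termination probability: "There is a 56% probability of early termination of the trial when the true response rate is 5"%. The Study Summary (Statistical Methodology) repeats the rule and the closing sentence.

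The Arm A paragraph, whose rule is to stop if none of 9 respond, ends with the same form of words: 63% at a true rate of 5%. There, 5% is the null rate.

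**The concern.** A Simon design's early-termination probability is normally quoted at the null rate, as the Arm A paragraph does. The Arm B paragraph uses a null of 20% throughout and then quotes this last figure at 5%, a rate that appears nowhere else in that paragraph. Either the probability or the rate must be wrong.

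The figure tells a reader how likely the arm is to stop after 12 patients if the combination adds nothing. Section 10.3 puts the expected response rate in refractory patients at 5%, so anyone reading about Arm B would take 56% as the stopping probability in exactly that situation. If the true figure is very different, the plan misdescribes how the arm would behave.

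**Working it through.** **Inputs** (section 10.2, Arm B): first stage n1 = 12; stop if responses are 2 or fewer (r1 = 2); total n = 25; final boundary r = 7; null rate 0.20; target rate 0.40; type I error 0.10; power 0.80. Stated early-termination probability: 0.56 at a true rate of 0.05. For Arm A: n1 = 9, r1 = 0, r = 2, n = 24, stated early-termination probability 0.63 at 0.05.

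**Formula.** Early termination at true rate p is P(X ≤ r1), with X ~ Bin(n1, p), that is, the sum over x = 0 to r1 of C(n1, x) p^x (1 − p)^(n1 − x).

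**Check of the method on Arm A.** P(X = 0) with n1 = 9, p = 0.05 is 0.95^9 = 0.630. This matches the stated 63%.

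**Arm B rule, 2 or fewer of 12:**

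| Responses | p = 0.05 | p = 0.20 |
|---|---|---|
| 0 | 0.5404 | 0.0687 |
| 1 | 0.3413 | 0.2062 |
| 2 | 0.0988 | 0.2835 |
| **Stop (2 or fewer)** | **0.9804** | **0.5583** |

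(Totals are from unrounded terms.) The stated 56% does not reproduce at 5%; it does at 20%. Solving P(X ≤ 2) = 0.56 for p gives p = 0.1995.

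**Could another boundary give 56% at 5%?** With 12 patients and p = 0.05, the stopping probabilities are 0.540 for 0 responses, 0.882 for 1 or fewer, 0.980 for 2 or fewer and 0.998 for 3 or fewer. None rounds to 56%. The nearest, stopping only on 0 of 12, is not the printed rule.

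**Is anything else in the Arm B design wrong?** For 2/12, 7/25, the exact probability of declaring activity (more than 2 responses in stage 1 and at least 8 of 25 overall) is:

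- at p = 0.20: 0.0991, consistent with the stated 10% type I error;
- at p = 0.40: 0.8151, consistent with the stated 80% power.

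A search for the optimal Simon design at 20% versus 40%, with type I error at most 0.10 and power at least 0.80, returns exactly 2/12, 7/25, with early termination 0.558 at the null. The same search at 5% versus 20% returns exactly 0/9, 2/24, with early termination 0.630, type I error 0.093 and power 0.805. Both printed designs are therefore sound for their own pair of rates; only the rate in Arm B's last sentence is out of place.

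**The case against.** The strongest reply is that 56% is the correct probability and only the condition is wrong. The paragraph's null is plainly 20%, the closing words mirror those for Arm A, and a careful reader can work out what was meant. On this view a 42-point error overstates a slip of one number. No boundary, sample size, error rate or analysis uses the sentence. The direction is also benign: at a true 5% the printed rule stops more often than stated, so protection against an inactive regimen is understated, not overstated. The more serious problem is that section 1.3.2 gives Group A the 20% versus 40% design and Group B the 5% versus 20% design, while section 10.2 and the Study Summary attach them the other way round.

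Most of this stands. The design was not miscalculated, the 42 points describe only the literal reading, and nothing operational changes. But the sentence is still false as printed, in two places, and nothing elsewhere in the document corrects it. Nor does resolving the arm labels repair it: the 2/12 rule gives 56% at 20% whichever arm carries it. If the two paragraphs simply changed places, the PD-1/PD-L1-naive arm would inherit a 5% condition that conflicts with its own 20% control rate in section 1.3.2.

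**Conclusion.** The concern holds. For the rule of stopping at 2 or fewer responses in 12, early termination has probability 98.0% at a true rate of 5% and 55.8% at 20%. The plan pairs the 20% value with the 5% rate. Against the literal statement the gap is 98 − 56 = 42 percentage points; against the evident intention it is one wrong rate.

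The result assumes only the boundary printed in section 10.2 and independent responses with a common rate, which is the basis of the Simon design itself. It does not depend on which arm the design belongs to.

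This should be corrected because it is a stated operating characteristic that the printed rule does not have. It also hides something a reader needs to see: 56% is the chance of stopping at a true rate of 20%, which section 1.3.2 names as the target for Group B.

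**What to change.** In section 10.2 and in the Study Summary (Statistical Methodology), state the 56% early-termination probability for the 2/12, 7/25 design at a true response rate of 20% instead of 5%. Leave 63% at 5% for the 0/9, 2/24 design.

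Tie each figure to its design, not just to an arm letter, and make the edit together with the reconciliation of the arm assignments across sections 1.3.2, 10.2, 10.3 and the Study Summary. Section 10.3 needs attention in the same pass, since it gives Group B a target of 40% where section 1.3.2 gives 20%.

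The cost of this point alone is one number in two places, with no redesign and no change to sample size or boundaries.
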